### 3.2. Exclusion Criteria

1. Patients who undergo asymptomatic screening test that is positive and remain asymptomatic during the eligible time window
2. Patients who have had one or more positive tests more than 5 days prior to enrollment but within 60 days of enrollment (ex. If a patient has a positive test 10 days prior to enrollment and then a second positive test the day referred for enrollment, that patient would be excluded. If a patient had a positive test 5 months ago, and then another positive test the day he/she was referred for enrollment, that patient would be eligible.)
3. Unable to take oral medication

4. Male patients with female partners of reproductive potential who are unable to maintain effective contraception during the recommended time period (during treatment and for 130 days after the final dose)
5. Symptoms requiring hospitalization or immediate referral to hospital
6. Taking bicalutamide, any systemic hormonal therapy, or camostat within one month of study entry
7. Known hypersensitivity to bicalutamide, or camostat, or its components.
8. On coumadin anticoagulation (because of drug-drug interaction with bicalutamide)
9. Self-reported past medical history of chronic liver disease or cirrhosis
10. Self-reported myocardial infarction within 6 months or past medical history of congestive heart failure with known ejection fraction < 40%
11. Taking any other investigational treatment for COVID-19 or COVID-19 prophylaxis (COVID-19 vaccines and treatments allowed under FDA Emergency Use Authorization are allowed.)

[figure not shown]

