### 4.2. Study treatments

#### 4.2.1. Camostat and Bicalutamide

Patients randomized to camostat and bicalutamide arm will receive 600mg of camostat mesilate (six 100mg tablets), four times a day on an empty stomach [one hour before a meal (e.g. 6:00, 11:00, 16:00, and 21:00)] and 150mg of bicalutamide daily for a total of 7 days. Bicalutamide will be given as three 50mg tablets.

Rationale for dose: Bicalutamide is well tolerated at 50mg and 150mg. It is frequently given at a dose of 150mg when used as a single agent, rather than the 50mg dose which is usually given in combination with medical or surgical castration. Bicalutamide 150mg

daily is approved for use in the European Union for the treatment of prostate cancer (European Medicines Agency, 2018). Bicalutamide has been extensively tested at a higher dose of 150 mg per day as monotherapy for prostate cancer, although it is not FDA-approved at this dose. Pharmacokinetic studies demonstrate an approximate doubling of the Cmax, Css and AUC and when bicalutamide is administered at this 3-fold higher dose.(Cockshott, 2004) Thus, we are using the higher dose bicalutamide of 150 mg/day compared to lower dose of 50 mg/day in order to achieve maximum androgen receptor blockade over the short 7-day exposure period proposed in this trial

Should any patient enrolled on the study miss a scheduled dose for whatever reason, the patient will be allowed to take the scheduled dose up to a maximum of 12 hours after that scheduled dose time. If greater than 12 hours, the missed dose should not be taken and the patient should take their allotted dose at the next scheduled time. Patients should also be advised to avoid conceiving for 3 months after the last dose of bicalutamide.

Rationale for duration of bicalutamide and camostat:

Both drugs are generally used for long periods of time, with bicalutamide safely given for years at a time. Trough concentrations of 150 mg/day bicalutamide at 7 days exceed the steady state trough levels of 50 mg/day bicalutamide after 28 days. Additionally, an increase in estradiol has been demonstrated at one week of starting bicalutamide at this dose. (Verhelst et al., 1994)

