Additionally, respiratory infections are commonly treated for up to 7 days. For example, the Infectious Disease Society of America (IDSA) guidelines for the recommendation of treatment of influenza is for 5 days of anti-viral therapy in outpatients, with consideration of longer duration for certain populations. Given this trial is in patients at least 60 years old and the severity of the disease, we believe a longer duration is warranted. This, in combination with the data presented above, is why we believe 7 days is safe, likely to be effective, and in line with other treatment paradigms.

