#### 6.2. Randomization

Once eligibility is confirmed, patients will be randomized to a treatment group in a 1:1 fashion and stratified by gender and by receipt of SOC drugs/vaccine. All patients must commence treatment within 72 hours of randomization.

Eligible patients will be entered on study centrally at the Sidney Kimmel Comprehensive Cancer Center at the Johns Hopkins University by the Lead Study Coordinator. All sites should call/email the coordinating center at [[contact]](mailto:[contact]) for registration. The Registration Form and Eligibility Worksheet will be supplied to each participating site.

Subjects who sign a consent form, but do not initiate protocol treatment for any reason (e.g., subjects who are screen failures), will be replaced and will not count towards our accrual goal. The Coordinating Center should be notified as soon as possible.

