### 6.5. Treatment period

Patients will be followed according to the study calendar (Section 10). Patients in all arms will have telemedicine or audio telephone call at day 3, 7, 21, and day 60 to assess toxicity and recovery. If patients are admitted to the hospital during follow up, we will get information from the medical records.

Patients will be instructed to monitor for emergency warning signs. This includes, but is not limited to: trouble breathing, persistent pain or pressure in the chest, new confusion, inability to wake or stay awake, bluish lips or face. If any of these occur, patients will be instructed to call 911 or go to her/his local emergency facility for further evaluation.

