#### 6.6. End of initial treatment

After 7 days of oral therapy, treatment will stop and patients will be followed as per section 10 (study calendar).

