## PHARMACOLOGY

Pharmacokinetics: Bicalutamide is well-absorbed following oral administration, although the absolute bioavailability is unknown. Co-administration of bicalutamide with food has no clinically significant effect on rate or extent of absorption.

Bicalutamide is highly protein-bound (96%). Bicalutamide undergoes stereospecific metabolism. The S (inactive) isomer is metabolized primarily by glucuronidation. The R (active) isomer also undergoes glucuronidation but is predominantly oxidized to an inactive metabolite followed by glucuronidation. Both the parent and metabolite glucuronides are eliminated in the urine and feces. The S-enantiomer is rapidly cleared relative to the R-enantiomer, with the R-enantiomer accounting for about 99% of total steady-state plasma levels.

Drug interactions: Clinical studies have not shown any drug interactions between bicalutamide and LHRH analogs (goserelin or leuprolide). There is no evidence that bicalutamide induces hepatic enzymes. In vitro studies have shown that R-bicalutamide is an inhibitor of CYP 3A4 with lesser inhibitory effects on CYP 2C9, 2C19 and 2D6 activity. Clinical studies have shown that with co-administration of bicalutamide, mean midazolam (a CYP 3A4 substrate) levels may be increased 1.5-fold (for Cmax) and 1.9-fold (for AUC). Hence, caution should be exercised when bicalutamide is co-administered with CYP 3A4 substrates. In vitro protein-binding studies have shown that bicalutamide can displace coumadin anticoagulants from binding sites. PT/INR should be closely monitored in patients concomitantly receiving coumadin anticoagulants and bicalutamide. Adjustment of the anticoagulant dose may be necessary

Females and Males of Reproductive Potential: Antiandrogen therapy may cause morphological changes in spermatozoa. Based on findings in animal reproduction studies and its mechanism of action, advise male patients with female partners of reproductive potential to use effective contraception during treatment and for 130 days after the final dose of bicalutamide. Based on animal studies, bicalutamide can lead to inhibition of spermatogenesis and may impair fertility in males of reproductive potential. The long-term effects of bicalutamide on male fertility have not been studied.

Geriatric Use: In two studies in patients given 50 or 150 mg daily, no significant relationship between age and steady-state levels of total bicalutamide or the active R-enantiomer has been shown.

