Hepatic Impairment: Bicalutamide should be used with caution in patients with moderate-to severe hepatic impairment. Bicalutamide is extensively metabolized by the liver. Limited data in subjects with severe hepatic impairment suggest that excretion of bicalutamide may be delayed and could lead to further accumulation. Periodic liver function tests should be considered for hepatic-impaired patients on long-term therapy. No clinically significant

difference in the pharmacokinetics of either enantiomer of bicalutamide was noted in patients with mild-to-moderate hepatic disease as compared to healthy controls. However, the half-life of the R-enantiomer was increased approximately 76% (5.9 and 10.4 days for normal and impaired patients, respectively) in patients with severe liver disease (n=4).

Renal Impairment: Renal impairment (as measured by creatinine clearance) had no significant effect on the elimination of total bicalutamide or the active R-enantiomer.

Formulation: Bicalutamide is prepared as round, film-coated green or white tablets containing standard excipients and 50 mg of the drug.

Storage and stability: All packages of bicalutamide should be stored securely in a dry place at room temperature.

Route of Administration: Bicalutamide is to be administered in tablet form as a once-daily oral dose. Patients should be instructed to take one 150mg pill once daily.

Supplier: Bicalutamide is commercially available

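### Section 4.2.1 advises avoiding conception for 3 months after bicalutamide, 38 to 41 days less than the 130 days set for men in exclusion 4 and section 8.2 (low severity)

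*Combined protocol and SAP*

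**What the plan says.** Three places in the protocol give a reproductive precaution after bicalutamide.

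- Section 4.2.1, after the missed-dose instructions: "Patients should also be advised to avoid conceiving for 3 months after the last dose of bicalutamide". The sentence covers patients in general and names neither sex.
- Section 3.2, exclusion 4, applies to men whose female partners could conceive and bars any man described by these words: "unable to maintain effective contraception during the recommended time period (during treatment and for 130 days after the final dose".
- Section 8.2, in the Pharmacology text on reproductive potential, tells sites to "advise male patients with female partners of reproductive potential to use effective contraception during treatment and for 130 days after the final dose of bicalutamide".

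On who is treated and for how long, section 4.2.1 says "Given this trial is in patients at least 60 years old" when it justifies the duration, and section 6.6 says "After 7 days of oral therapy, treatment will stop". Women are eligible under section 3.3. Neither period is derived anywhere in the protocol, and nothing limits the 3-month advice to a particular group.

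**The concern.** Exclusion 4 calls 130 days the recommended period, and section 8.2 gives the same figure. The shorter figure stands in the section that tells sites how to give the drugs, which is where staff would naturally look when counselling a patient. A man could be found eligible because he can use contraception for 130 days and then be told that 3 months is enough. If he followed that advice he would stop early by the protocol's own standard. What is at stake is the consistency of a safety instruction. The trial's estimates are not affected.

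**Working it through.** **Inputs.** Section 4.2.1: 3 months after the last dose. Exclusion 4 and section 8.2: 130 days after the final dose. Section 6.6: treatment stops after 7 days. Section 8.2, Hepatic Impairment: half-lives of the active enantiomer of "5.9 and 10.4 days for normal and impaired patients", where the impaired group is four patients with severe liver disease. Sections 3 and 4.1: 40 patients randomized 1:1, so 40 / 2 = 20 treated.

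**Length of 3 months.** Over every start date from 2020 to 2024, three calendar months last 89, 90, 91 or 92 days.

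**Gap.** Gap = 130 − length of 3 months.
- Longest case: 130 − 92 = 38 days, and 38 / 130 = 29%.
- Shortest case: 130 − 89 = 41 days, and 41 / 130 = 32%.
- With an average month of 30.4375 days: 130 − 3 × 30.4375 = 38.7 days.

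**On the study clock,** assuming the last dose is on day 7:
- The 3-month advice ends between day 7 + 89 = 96 and day 7 + 92 = 99.
- The 130-day period ends on day 7 + 130 = 137.

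**Drug remaining when the 3-month advice ends.** Fraction of the end-of-dosing level = 0.5^(days / half-life).

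| Half-life | 89 days | 92 days |
|---|---|---|
| 5.9 days | 0.0029% | 0.0020% |
| 10.4 days | 0.27% | 0.22% |

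The second row is an upper bound of little practical relevance, because exclusion 9 removes patients with self-reported chronic liver disease or cirrhosis. In either row almost no drug is left. This does not show which period is right: section 8.2 bases its advice to men on animal reproduction findings and the drug's mechanism, and does not derive 130 days from plasma levels.

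**Who is reached.** The sentence in 4.2.1 covers both sexes. With a minimum age of 60, advice about conception matters almost only for men with younger partners, the group given 130 days in the other two places. The documents give no count of such men; it can only be some part of about 20.

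**The case against.** The best reply is that the statements can stand together: 3 months as a general minimum, 130 days as a stricter rule for a subgroup. A man who keeps to 130 days satisfies both, and the word conceiving may have been written with women in mind. This is a fair account of how the sentence may have arisen. But the text states no such division, and in a population aged 60 or over a rule meant only for women would have almost nobody to apply to. As written, the sentence also covers men and gives them the shorter period.

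The second reply is that the longer rule is already in force. Section 6.2 says "Once eligibility is confirmed, patients will be randomized to a treatment group", so each affected man is screened against 130 days first, and section 8.2 is itself an instruction to advise these men correctly. This stands, and it is a main reason for the low rating. It leaves two different periods for sites to choose from.

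Exclusion 4 and section 8.2 are worded so alike that they may share one source, so their agreement is not independent evidence for 130 days. The case here needs only that the protocol should give one figure.

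A reader might also infer that follow-up ends too early to catch the error. Section 6.5 says "Patients in all arms will have telemedicine or audio telephone call at day 3, 7, 21, and day 60". All of these calls come before day 96, when the two periods first diverge, so each is a chance to correct the advice. The protocol assigns none of them to contraception counselling, but their timing is not a defect.

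**Conclusion.** The inconsistency is real and of low severity. Section 4.2.1 gives all patients a period 38 to 41 days shorter than the one that exclusion 4 and section 8.2 set for men whose partners could conceive. The gap in days is calendar arithmetic; the study-day figures assume uninterrupted dosing to day 7. That the sentence reaches mainly men is an inference from the age limit.

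Two stronger readings are not supported. The first is that patients are put at measurable risk: the residual drug fractions are negligible and the documents give no other measure of harm at 3 months. The second is that patients are in fact being told the wrong period: the consent pages and patient instructions are not in the reviewed copy, so no mismatch in them can be claimed. The primary endpoint, the power statement and the planned analyses are unaffected.

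**What to change.** In section 4.2.1, change the period in the conception sentence from 3 months to 130 days and keep it addressed to all patients. Add a sentence saying that men with female partners of reproductive potential should use effective contraception while on treatment and for 130 days after the final dose. Do not replace the general sentence with a men-only one: it is the only advice on avoiding conception that is not limited to men, women are eligible, and section 8.2 warns of fetal harm. Then check that the patient instructions give the same period.

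The cost is a line or two of amendment text and that check. No visit, test, sample-size or analysis change is needed.

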#### **4.3. Supportive care guidelines and general concomitant medications**

In general, concomitant medications and therapies deemed necessary for the supportive care and safety of the subject are allowed, provided that their use is documented in the medical records. The administration of any other therapies intended to treat the primary condition are permitted if considered the standard of care. The use of other concurrent investigational drugs is NOT allowed during the screening and treatment period. Patients should receive appropriate supportive care measures as deemed necessary by the Investigator and treating physicians.

#### **4.4. Drug compliance documentation**

Compliance will be recorded on a Diary of Treatment.

#### **4.5. Prohibited and restricted therapies**

- Any COVID-19 investigational agent (e.g. hydroxychloroquine or chloroquine) during the screening and treatment period, or within 30 days of enrollment.
- Coumadin (warfarin) anticoagulation during treatment period

#### 4.6. Drug dispensing

Study drug can be picked up in person or shipped to the patient directly. If study drug is shipped, the temperature will be monitored during shipment. Study staff will call the patient to ensure that shipment was received in good condition at the patient's home, and instruct patient to keep and return all empty, partially empty, or full bottles/blisters to the site at next visit for drug reconciliation. This call, including verbal confirmation of receipt by the patient, will be properly documented in the medical record. If COVID-19 precautions prevent the return of used/unused study drug supplies to the site, then study staff will review the remaining pills during a telemedicine visit with a photo or video documentation of drug destruction (using a drug disposal pouch) that can be sent to the IND Sponsor (or designee). Undelivered supplies should be returned to the clinical site.

### 5. Dosing Delays/Dose Modifications

If patients are unable to tolerate 600mg of camostat four times a day, the dose will be reduced to 300mg four times a day. If patients are unable to tolerate 300mg four times a day, treatment will decrease to 200mg three times a day (approved dose in Japan). If patients are unable to tolerate that dose, treatment will be stopped.

If patients are unable to tolerate 150mg of bicalutamide, the daily dose will be reduced to 100mg. If patients are unable to tolerate 100mg, the dose should be reduced to 50mg. If 50mg is unable to be tolerated, treatment should stop.

### 6. Study Activities

#### 6.1. Screening period

All patients must sign a written informed consent form before any study specific procedures are performed. If the patient meets eligibility and screening requirements, he/she will be randomized to one of two arms. All required treatment study procedures and assessments must be initiated within 72 hours of the baseline screening evaluation.

#### 6.2. Randomization

Once eligibility is confirmed, patients will be randomized to a treatment group in a 1:1 fashion and stratified by gender and by receipt of SOC drugs/vaccine. All patients must commence treatment within 72 hours of randomization.

Eligible patients will be entered on study centrally at the Sidney Kimmel Comprehensive Cancer Center at the Johns Hopkins University by the Lead Study Coordinator. All sites should call/email the coordinating center at [[contact]](mailto:[contact]) for registration. The Registration Form and Eligibility Worksheet will be supplied to each participating site.

Subjects who sign a consent form, but do not initiate protocol treatment for any reason (e.g., subjects who are screen failures), will be replaced and will not count towards our accrual goal. The Coordinating Center should be notified as soon as possible.

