## 4. Treatment Plan

### 4.1. Study design

This will be a randomized, open-label study to determine if camostat+ bicalutamide decreases the proportion of people with COVID-19 who require hospitalization, compared to historical controls. Patients with symptomatic COVID-19, diagnosed as outpatients, will be randomized 1:1 stratified by gender and receipt of SOC drugs/vaccine, to treatment with standard of care alone or with camostat+bicalutamide . The schema is shown below:

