## 10. Study Calendar

	Day of study										
	Baseline/ screening	Treatment							Follow up ( $\pm$ 3 days)		
		-3 to 0	1	2	3	4	5	6	7 &	21	60
Eligibility	X										
Consent	X										
Randomization and drug dispensing*	X										
COVID-19 symptoms	X ^				X				X	X	X
Follow-up visit (can be in person, via telephone or via telemedicine)**				X					X	X	X
Review of medical record for hospitalization, death, etc a								X			
Both arms standard of care		X	X	X	X	X	X	X			
Experimental arm: Bicalutamide + camostat Treatment		X	X	X	X	X	X	X			
Adverse events, con meds (including OTC medications), new infections***			X						X	X	X
COVID-19 nasopharyngeal swab ^^	X								X	X	
Clinical and study blood collection (CMP b , CBC and differential, coagulation, d-dimer, CK, CRP, ESR, ferritin) ^^		X							X	X	
Ultrasensitive PSA + sex hormones c^^	X								X	X	
COVID-19 RNA testing (quantitative and qualitative) from blood, oral samples for research) ^^	X								X	X	
Additional research blood draw (1 tube) ^^	X								X	X	
SARS-CoV-2 antibody analysis ^^	X								X	X	

\*Study drug may be shipped to the patient. See section 4.6 for information relevant to drug dispensing.

Review of remaining pills and Study Drug Patient Diary may be conducted during a telemedicine visit.

Copies of the Study Drug Patient Diary may be submitted to study staff by phone, email, fax, or mychart

\*\*If patients are admitted, we will get information from the medical record.

\*\*\*Any new infection that occurs on study will be recorded. The site of infection and the source of culture (ie BAL, tracheal aspirate, sputum, blood, urine, etc.) will be recorded as well.

aThe following will be recorded daily (as available) from hospital records: symptoms (see Appendix A), temperature, heart rate, respiratory rate, systolic blood pressure, diastolic blood pressure, oxygen saturation, height, weight, oxygen requirements and supplementary oxygen use, procedures (including intubation, renal replacement therapy, vasopressor/inotropic support, ECMO, etc), intermediate care unit duration, intensive care unit duration

bCMP: Na, K, Cl, BUN, Cr, Ca, Tot Protein, Alb, bilirubin, AST, ALT, Alk phos, CO2

cSex hormones: estradiol, free testosterone, total testosterone, FSH, LH

& Day 7 labs may be collected +/- 3 days

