## 11. Statistical considerations

Our null hypothesis is that 20% of patients will require hospitalization by day 28. This is based on internal data (from [name] EPIC analysis team at Johns Hopkins Hospital) that demonstrates an overall hospitalization rate of 14% and a hospitalization rate of 18-20% in patients 60 years old and older. We expect that each of the investigational treatment will reduce it to 2% or lower.

The sample size of 20 in each investigational arm is determined based on the comparison to the control arm. The design gives us 80% power to detect a decrease in hospitalization rate from 20% in the control arm to 2% in the treatment arm, based on a one-sided Fisher's exact test with type I error of 0.25.

If we observe 1 or less patient hospitalized within 28 days since randomization in an investigational arm, we reject the null rate of 20% in favor of 4% or less hospitalization rate with that treatment. **Table 1** lists the 90% confidence intervals for various scenarios of observed proportion of hospitalized patients. **Table 2** shows the probability of observing 1 or less hospitalized patient under various true rates. If the true rate is 20% in Arm B or Arm C, the chance of observing only 1 or less hospitalization is low at 7%; and that chance is greater than 80% if the true hospitalization rate is 4% or lower. Given this is a small study, and the true effect size is unknown, the estimates and safety generated in this trial will be used to inform power calculations of a larger, confirmatory trial.

**Table 1.** Confidence intervals for various observed proportions of hospitalized patients in each arm.

Observed # of hospitalizations (out of 20)	Observed hospitalization rate	90% CI (Wilson method)
0	0%	[0, 11.9%]
1	5%	[1.1%, 19.6%]
2	10%	[3.4%, 26.2%]
3	15%	[6.2%, 32.2%]
4	20%	[9.3%, 37.8%]
5	25%	[12.7%, 43.2%]
6	30%	[16.4%, 48.4%]
7	35%	[20.2%, 53.3%]
8	40%	[24.2%, 58.1%]

**Table 2.** True hospitalization rate and probability of observing 1 or less hospitalization for each arm.

True hospitalization rate	Probability of observing 1 or less hospitalization (out of 20 patients)
1%	98%
2%	94%
3%	88%
4%	81%
5%	74%
6%	66%
10%	39%
15%	18%
20%	7%
25%	2%

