### 11.1. Analysis of primary endpoint:

The % of patients admitted to the hospital or died will be estimated for each arm as the proportion of patients who are hospitalized or die by day 28 since randomization along with 95% confidence interval. The secondary analysis of comparison between arms will be conducted using Fisher's exact test.

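### Patients who never start treatment are replaced even if already randomized, and no analysis set is defined, so an admission before the first dose could drop out of the 1-in-20 success rule

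*Combined protocol and SAP*

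**What the plan says.** Section 6.2 sets the replacement rule: "Subjects who sign a consent form, but do not initiate protocol treatment for any reason (e.g., subjects who are screen failures), will be replaced". The sentence continues that these subjects "will be replaced and will not count towards our accrual goal". The test is whether treatment was started, not whether the patient had been randomized.

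The same section allows a gap after randomization: "All patients must commence treatment within 72 hours of randomization". The calendar in Section 10 puts the row "Randomization and drug dispensing" in the baseline column, days -3 to 0, with treatment from day 1. Section 4.6 adds a practical reason for delay: "Study drug can be picked up in person or shipped to the patient directly".

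The endpoint clock starts at randomization. Section 11 gives the success rule: "If we observe 1 or less patient hospitalized within 28 days since randomization in an investigational arm, we reject the null rate of 20" per cent. Section 11.1 estimates, for each arm, the "proportion of patients who are hospitalized or die by day 28 since randomization". Neither section names an analysis set or says how a replaced patient is handled. Section 6.9 keeps patients who discontinue treatment in follow-up but does not mention those who never start. Section 7.5 collects adverse events only from the first dose.

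**The concern.** A patient who deteriorates and is admitted in the days between randomization and first dose has had the primary event and has not started treatment. Under Section 6.2 that patient can be replaced. If replacement also means leaving the analysis, an event is removed because it happened early, and a patient who got through the interval without an admission takes the place. The loss is related to the outcome.

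The trial is exposed to this because it is open-label, has 20 patients per arm, and decides success on 1 event versus 2.

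Removal may also be unequal between arms. Controls have no study drug to start, so in practice the rule may act mainly on the drug arm. That is an inference: Section 4.1 describes randomization "to treatment with standard of care alone or with camostat+bicalutamide", and the 72-hour sentence covers all patients, so both arms could be meant.

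**Working it through.** **Inputs from the documents.** 20 patients per arm; success at 1 or fewer events; null rate 20%; target 4% or lower; one-sided Fisher's exact test at 0.25 for 20% versus 2% (Section 11); at most 72 hours from randomization to treatment (Section 6.2).

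**Input assumed.** f, the share of 28-day events that fall before the first dose. The documents do not give it, so a range is shown. Every patient with a pre-dose event is taken to be removed and replaced.

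**The plan's own figures.** P(X ≤ 1) for a binomial with n = 20 is 6.9% at 20% and 81.0% at 4%, matching the 7% and 81% in Table 2 of Section 11. Full enumeration of the Fisher test for 20% versus 2% gives 80.3% power, matching the stated 80%. Its actual size with both rates at 20% is 15.7%.

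**Effect on the single-arm rule.** With true rate p = 0.20, the rate among patients who start treatment is

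q = p(1 − f) / (1 − pf).

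For example, f = 0.10 gives 0.18 / 0.98 = 0.1837. The chance that an inert drug meets the rule is then P(X ≤ 1 | 20, q). The chance that at least one of 20 randomized drug-arm patients has a pre-dose event is 1 − (1 − 0.2f)^20.

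| f | q | P(X ≤ 1) | P(at least one pre-dose event) |
|---|---|---|---|
| 0 | 0.2000 | 6.9% | 0 |
| 5% | 0.1919 | 8.1% | 18% |
| 10% | 0.1837 | 9.5% | 33% |
| 25% | 0.1579 | 15.3% | 64% |

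As a reference point, events spread evenly over 28 days with the full 72 hours used give f = 3/28 = 10.7%, q = 0.1825 and a 9.7% chance.

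**Effect on the between-arm Fisher test** (20 versus 20, one-sided 0.25, inert drug):

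| f | Removal in drug arm only | Removal in both arms |
|---|---|---|
| 0 | 15.7% | 15.7% |
| 5% | 17.1% | 15.4% |
| 10% | 18.8% | 15.2% |
| 25% | 24.6% | 14.3% |

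Drug-arm-only removal raises the error but keeps it under the nominal 0.25. Removal in both arms does not raise it. The comparison with the fixed 20% rate gains in either case.

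**One patient.** Suppose the drug arm has one pre-dose admission and one later admission, and controls have 4/20. Counting everyone gives 2/21, which misses the rule (one-sided Fisher p = 0.307). Replacing the first patient gives 1/20, which meets it (p = 0.171).

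**The case against.** The strongest reply is that Section 6.2 concerns accrual, not analysis. It says who is replaced and who counts toward the target; it does not say who leaves the analysis, and its only example is a pre-randomization loss. Sections 11 and 11.1 count from randomization, admissions are found by querying medical records (Section 6.7), and survival runs from randomization (Section 6.12). None of that depends on dosing. This is a fair reading, and exclusion is no more than what the text allows. But no sentence requires a replaced patient to be counted, so the question stays open.

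The second reply is about size, and most of it stands. Section 3.2 excludes patients whose symptoms require hospitalization. Section 6.1 starts a 72-hour clock at baseline screening, so the gap may be shorter than Section 6.2 allows. Under the even-spread assumption a one-day gap gives about 7.7% and a two-day gap 8.7%, against 6.9%. The 25% row is an upper illustration with no support in the documents.

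Third, the Fisher result does not always flip. With 5/20 controls both 2/21 (p = 0.18) and 1/20 (p = 0.09) pass at 0.25; with 3/20 even 1/20 does not (p = 0.30). That is correct for the Fisher test, which Section 11.1 makes secondary. The single-arm rule does not depend on the controls, and 2 events miss it whatever the denominator.

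Finally, Section 11 presents the study as input to a larger trial. That lowers the stakes but does not excuse leaving open which patients enter the go decision.

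**Conclusion.** The concern holds and should be fixed. As written, the plan permits replacement of randomized patients for a reason that can be the primary event itself, and it does not define who is analysed. It does not expressly exclude such patients.

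The likely size is modest. If every pre-dose event is removed, the false-success chance at a true 20% rate rises by 1.2 percentage points when 5% of events are pre-dose (8.1% − 6.9%) and by 2.6 points when 10% are (9.5% − 6.9%). Larger shares are hard to reconcile with the eligibility criteria and the short gap. Inflation of the between-arm test further requires removal mainly from the drug arm, which is an inference, and even then the error stays within 0.25. Confidence is high that the gap in the text exists; the size rests on an assumed f.

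**What to change.** - In Section 6.2, limit replacement to subjects who fail before randomization.
- In Section 11.1, state that the primary analysis includes every randomized patient in the assigned arm, with events counted from randomization whether or not study drug was started.
- If extra patients are enrolled to reach 20 treated, keep the untreated ones in the primary analysis and state the success threshold for the larger arm.
- Make a treated-only analysis a sensitivity analysis.

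The threshold choice, with exact binomial figures:

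| Patients in arm | At most 1 event, true 20% | At most 1 event, true 4% | At most 2 events, true 20% |
|---|---|---|---|
| 20 | 6.9% | 81.0% | not the plan's rule |
| 21 | 5.8% | 79.6% | 17.9% |
| 22 | 4.8% | 78.1% | 15.5% |

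Keeping the limit at 1 event costs 1.4 points (81.0% − 79.6%) with 21 patients, or 2.9 points (81.0% − 78.1%) with 22, of the chance of success at a true 4% rate. Raising it to 2 would more than double the false-success chance. The other cost is slight dilution of the estimate if a few randomized patients never start drug. The text change is one sentence in Section 6.2, one in Section 11.1, and a line on the threshold. It should be made before outcomes are known.
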